The results of other studies [de Lateur et al 1991; Lee et al. 2001; Kwon et al. 2015; Schroeder and Hollander 2018] showed that heel elevation did not significantly change the LL in the female subjects evaluated.

None of the studies reported above take into consideration the time factor. In fact, all the studies have evaluated the immediate changes induced by heel raising. Women who complain of lower back pain when wearing high-heeled shoes rarely experience pain as soon as they start wearing them.

The objective of the research arises from these considerations.

The aim of this study (primary outcome) is to investigate whether wearing high-heeled shoes for at least 2 hours modifies the spinopelvic parameters compared to the barefoot condition and as soon as the shoes are worn.

The secondary outcome will be to verify in the sample analyzed whether there are different behaviors between the subgroups of those who have complained in their anamnesis and those who have never complained of lower back pain when using high-heeled shoes for a few hours.

MATERIALS AND METHODS

Location of the study

Spine Center and OSCE (Osteopathic Spine Center Education), [name]

Population

Students of the OSCE osteopathy school

Sample size

Not having found similar studies in the literature, we prefer to start as a pilot study with the recruitment of approximately 30 female subjects. This number represents a good compromise between the possibility of finding a normal distribution and the feasibility of the study.

Recruitment

Recruitment will be carried out by announcing on the bulletin board and presenting the study project in the classroom of the OSCE osteopathy school.

Following the ethical principles of the Declaration of Helsinki, a paper information will be provided where there will be an explanation of the intent and purpose of the study to all subjects before their participation; furthermore, together with the information, a paper consent will be provided on which to obtain consent written informed voluntary consent to participate in the study and consent to the use of data through privacy information.

Inclusion criteria

- female subjects aged between 20 and 40 years
- usual users of shoes with heels at least 7 cm high, with a frequency of at least twice a week and/or more than 3 hours/week as proposed by a previous study (de Oliveira Pezzan et al. 2011);

Exclusion criteria

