- structural or neurological anomalies that may prevent from standing, for approximately 2 hours, with shoes having a heel (difference between the heel and the plateau) of at least 7 cm high;

Methods

A three-dimensional analysis of the posterior surface will be performed with the Formetric 4D® rasterstereographic device (Diers International GmbH, Schlangenbad, Germany). Participants will be asked to complete the informed consent form after reading the information. Furthermore, consent to the processing of data will be requested after reading the Privacy form, confirming their participation in the study.

Participants will be given a questionnaire which investigates:

- Age, weight, height of the participants;
- Any pain in the spine (measured by NPS) usually reported by subjects after using high-heeled shoes;
- Type of profession;
- Frequency with which the subjects wear the heeled shoe (how many hours per week);
- Heel height of the shoe with which they participate in the clinical study;
- Any spinal pain (measured by NPS) after wearing heeled footwear for the study period.

This last data will be filled in at the end of the evaluation.

For the evaluation of the secondary outcome, on the basis of the data from the medical history sheet, the sample will be divided into two groups:

- 1) The first group (group A, ASYMPTOMATIC) includes subjects who during daily life do not report spinal pain after wearing high-heeled shoes;
- 2) The second group (group S, SYMPTOMATIC) is made up of participants who usually complain of more or less intense pain after using the shoe.

Heel type

The subjects will be asked to bring their own pair of shoes with a heel that is at least 8.7 cm, the average height reported by the work of Schroeder and Hollander (2018), where average height means the difference between the height of the heel and the height of the raised part at the forefoot level (plateau). A particular heel width will not be required, because it seems that the height of the heel influences muscle activation, in particular the paravertebral muscles, while the width of the heel has no significant effects on them (Han 2015).

Conversely, amplitude has a greater influence on balance when standing and while walking.

Measurement method

Positioning with respect to the measurement system will be carried out according to the indications provided by the supplier.

To standardize the position the subjects will be prepared for the analysis as follows:

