1. standing, back to the detection system, in a relaxed posture with knees fully extended with bare feet on the floor (neutral position)
2. bare torso with trousers and briefs lowered to mid-buttock;
3. in the case of long hair, it will be required to tie it with suitable means (cap, hair clips, hair ties, etc.) so that the neck is visible up to the hairline;
4. Rings, watches and necklaces will be removed to avoid any interference with the light lines (necklaces in particular increase this probability).

A three-dimensional analysis of the posterior surface is performed with the Formetric 4D® rasterstereographic device (Diers International GmbH, Schlangenbad, Germany) [9-15].

[figure not shown]
The device, already supplied at the Spine Center rehabilitation center in Bologna and made available free of charge for study, is non-invasive and non-dangerous. The analysis of the spine curve with rasterstereography is carried out with a purely optical modality.

The protocol

- 1) first evaluation in neutral position with bare feet (T0)
- 2) second evaluation in neutral position wearing shoes (T1);
- 3) third evaluation like the previous one but at least 2 hours apart, in which it will be required to remain standing still or walk (T2).

Parameters detected

- 1) Flexion of the antero-posterior trunk (trunk inclination – TI) measured as the angle between the vertical and the line that passes through the prominent cervical vertebra (VP) and the line that connects the two dimples (DM);
- 2) pelvic inclination angle (PI), i.e. the angle between the vertical and the tangent to the lumbosacral junction (ILS);
- 3) ITL-ILS lordotic angle, measured between the tangents of the thoracolumbar junction (ITL) and the lumbosacral junction (ILS);
- 4) ICT-ITL kyphotic angle, measured between the tangents of the cervicothoracic junction (ICT) and the thoracolumbar junction (ITL);
- 5) lumbar arrow (FL) (horizontal distance in millimeters of the lumbar spine from the virtual vertical line that passes through the kyphotic apex) ;
- 6) cervical arrow (FC) (horizontal distance in millimeters of the cervical spine from the virtual vertical line that passes through the kyphotic apex).

Statistic analysis

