A descriptive analysis of the population will be performed to determine the mean values and standard deviations (SD) of both the combined group and the subgroups A and S. T-tests for independent data will be used to verify whether there are any significant differences between the two subgroups .

The distribution of the data will be verified using graphical representation. If the distribution is normal ($p <0.05$) for the comparison between T1 vs T2 the t-test for paired data will be used and between the subgroups (T1S vs T1A and T2S vs T2A) t-test for independent data with statistical significance accepted for p values <0.05 . ANOVA will be used to simultaneously compare the pre and post of both groups.

If the data does not have a normal distribution ($p >0.05$) the Wilcoxon test will be used for the comparison between the T1 vs T2 data of the total group and the Mann-Whitney U test for the comparison between subgroups (T1S vs T1A and T2S vs T2A). The Friedman test will be used to simultaneously compare the pre and post of both groups.

Risks

The risks are quite limited given that the shoes worn are those owned by the tested subject, therefore it is assumed that they are used to wearing them, and they are not asked to perform movements at risk of sprains or falls.

Benefits

Being able to identify the spino-pelvic parameters that predispose to spinal symptoms, when wearing high heels, could help prevent the related pathology/symptoms through postural re-education or muscle strengthening exercises.

Costs

The use of the Formetric will be given free of charge and any related expenses (paper, color cartridges, etc.) will be borne by the Spine Center.

References

de Lateur BJ, Giacconi RM, Questad K, Ko M, Lehmann JF. 1991. Footwear and posture: compensatory strategies for heel height. *Am J Phys Med Rehabil* 70:246–254

de Oliveira Pezzan PA, Joa˜o SMA, Ribeiro AP, Manfio EF. 2011. Postural assessment of lumbar lordosis and pelvic alignment angles in adolescent users and nonusers of high-heeled shoes. *J Manip Physiol Ther* 34:614–621

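### Does the primary question need one named parameter, or a multiplicity adjustment across the six spinal measurements?

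*Combined protocol and SAP*

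**What the plan says.** The last paragraphs of the Introduction set the primary outcome: whether wearing heels for at least two hours "modifies the spinopelvic parameters compared to the barefoot condition and as soon as the shoes are worn". The parameters are in the plural; no single one is named, and the term spinopelvic is not tied to a list.

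The Parameters detected section gives six measurements: trunk inclination, pelvic inclination, lordotic angle, kyphotic angle, lumbar arrow and cervical arrow. They are not ranked. The last, "cervical arrow (FC) (horizontal distance in millimeters of the cervical spine", is not an obvious spinopelvic measure.

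The Statistic analysis section says that, for normally distributed data, "for the comparison between T1 vs T2 the t-test for paired data will be used", with the Wilcoxon test otherwise, and "with statistical significance accepted for p values <0.05". It gives no hierarchy, no adjustment and no rule for how many parameters must change.

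The Sample size section describes the scale: "we prefer to start as a pilot study with the recruitment of approximately 30 female subjects". The comparison of women with and without heel-related pain is labelled secondary in the Introduction ("The secondary outcome will be to verify in the sample analyzed whether there are different behaviors between the subgroups") and again under Methods ("For the evaluation of the secondary outcome").

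**The concern.** The aim reads as one yes/no question, yet six tests at 0.05 feed into it and nothing says how they combine. If one parameter gave p = 0.03 and the other five did not reach 0.05, the plan would not settle whether the primary outcome was positive. The Introduction describes a literature split over whether lordosis rises, falls or stays the same, so two readers could draw different conclusions from the same results.

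If any one significant parameter were enough, the chance of a false positive answer would be well above the 5% that the stated threshold suggests. The usual remedies are to name one primary parameter or to adjust across the six.

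**Working it through.** **Plan's own figure.** None. The documents give no family-wise error rate, power or calculated sample size.

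**Inputs from the documents.** Six parameters (Parameters detected); 0.05 per test and paired tests of T1 against T2 (Statistic analysis); about 30 women (Sample size).

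**Assumptions.** Two-sided tests. A common correlation r between the parameters' T1-to-T2 changes, varied from 0 to 0.95 because the documents give none. Three parameters as an alternative count of what is spinopelvic.

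**1. Any one significant parameter counts, no true change, independent parameters.** The chance of at least one p < 0.05 is 1 − 0.95^k.
- k = 6: 1 − 0.95^6 = 0.265
- k = 3: 1 − 0.95^3 = 0.143

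**2. The same with correlation.** For k equicorrelated normal statistics, the chance is 1 − ∫ φ(u) [Φ((1.96 − √r·u)/√(1−r)) − Φ((−1.96 − √r·u)/√(1−r))]^k du.

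| r | six parameters | three parameters |
|---|---|---|
| 0 | 26.5% | 14.3% |
| 0.5 | 20.7% | 12.5% |
| 0.7 | 16.4% | 10.9% |
| 0.9 | 10.8% | 8.4% |
| 0.95 | 8.9% | 7.3% |

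Simulated paired t-tests at n = 30 agree: for six parameters, 26.4%, 20.9%, 16.8%, 11.0% and 9.0% in the same order.

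Independence is unlikely. By their definitions, pelvic inclination and the lordotic angle share the lumbosacral junction, the lordotic and kyphotic angles share the thoracolumbar junction, and the two arrows are measured from the same vertical line through the kyphotic apex. The top row is therefore best read as an upper bound.

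**3. Each parameter reported as its own result.** Each test keeps its 5%. If nothing changed, the expected number of false positives among six is 6 × 0.05 = 0.3, a figure any reader can allow for when all six are shown.

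**4. Price of adjusting.** Noncentral t power, n = 30, assumed standardised paired effect 0.5 (noncentrality 0.5 × √30 = 2.74):
- at 0.05: 75%
- at 0.05/6 = 0.0083, the first Holm step over six: 47%
- at 0.05/12 = 0.0042: about 37%

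The last line matters because the aim has two contrasts, T2 against barefoot (T0) and T2 against shoes just put on (T1). If both were primary for all six parameters, there would be 12 p-values. With six tests, the effect detectable with 80% power rises from 0.53 to 0.68 standard deviations of the change.

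**5. Reporting estimates instead.** A 95% interval for each mean change has half-width t(0.975, 29)/√30 = 2.045/5.477 = 0.37 standard deviations of the change, with no multiplicity penalty.

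**The case for a change.** The strongest case for a change is that the plan is not purely descriptive. It declares a primary outcome, words it as a single question and sets a significance threshold. A sentence naming a primary parameter, or calling the analysis exploratory, would cost no participants or visits and would remove the ambiguity before data are seen. Naming one parameter would not reduce that parameter's power. Even at a correlation of 0.9, six parameters under an any-one rule would give about 11%, roughly twice the nominal level.

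Much of this stands. The combining rule is absent, and the arithmetic is right under its stated condition. A clarifying sentence would be good practice.

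It does not establish that the planned analysis is wrong. The plan does say what counts as a change in a given parameter: a paired test at 0.05. Only the step from six results to one answer is unstated, and the plural in the aim fits six separate answers at least as well as one. The remedies also point in different directions. Choosing one parameter is a scientific judgement on which the documents give no preference. Holm costs much of the power of a study this small. Declaring the pilot exploratory leaves the tests as they are.

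The Benefits section, which hopes for "Being able to identify the spino-pelvic parameters that predispose to spinal symptoms", does not help either side. It concerns symptoms, closer to the secondary comparison than to change between T1 and T2.

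**Conclusion.** No change to the plan follows. The absence of a primary parameter and of a combining rule is a missing detail in a small pilot, not an error in its analysis. The inflation (26.5% with six independent parameters, about 11% at a correlation of 0.9, about 9% at 0.95) needs an any-one-counts rule that the plan neither states nor excludes, together with correlations it does not give. Under parameter-by-parameter reporting each test stays at 5%.

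All six parameters are listed in advance, the list is short, and nothing suggests selective reporting. Analysts can fill the gap by reporting all six with estimates and 95% intervals, making no overall yes/no claim from an isolated p-value, and reading the subgroup tests in the same exploratory spirit. Formal adjustment would be a debatable trade at n = 30: first-step power falls from about 75% to 47% over six tests, or about 37% over 12, at an assumed effect of 0.5.

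The conclusion rests on the pilot being read as a pilot. If a write-up presented one significant parameter out of six as proof that heels alter spinal posture, the concern would apply to that claim.

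### Friedman has no group factor and the ANOVA names no interaction, so a difference in change between groups S and A has no valid test in one branch and an undefined one in the other

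*Combined protocol and SAP*

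**What the plan says.** The primary aim, at the end of the Introduction, is whether at least two hours in heels "modifies the spinopelvic parameters compared to the barefoot condition and as soon as the shoes are worn". The secondary outcome is to establish "whether there are different behaviors between the subgroups of those who have complained in their anamnesis" and those who have not. In Methods the groups are formed from history: "on the basis of the data from the medical history sheet, the sample will be divided into two groups", A (asymptomatic) and S (symptomatic). The protocol section sets three measurements: barefoot (T0), shoes just put on (T1), and at least two hours later (T2).

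The Statistic analysis section gives two kinds of test involving the groups:

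- **At single times.** If the data are normal: "between the subgroups (T1S vs T1A and T2S vs T2A) t-test for independent data". If not: "the Mann-Whitney U test for the comparison between subgroups (T1S vs T1A and T2S vs T2A".
- **Group and time together.** If the data are normal: "ANOVA will be used to simultaneously compare the pre and post of both groups". If not: "The Friedman test will be used to simultaneously compare the pre and post of both groups".

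Pre and post are not tied to T0, T1 or T2. No ANOVA factor or interaction is named, and no test on a change score appears.

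**The concern.** The primary aim concerns how posture is modified over T0, T1 and T2. Different behaviour between subgroups is then most naturally read as a different modification. A test at T1 or T2 alone compares levels. That is a fair question about posture in heels, but because the groups are defined by history it cannot separate posture the women already had from their response to the shoes.

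The sentence joining group and time should therefore carry the secondary question. In the non-normal branch it names a test that cannot do so. A significant pooled Friedman result would show only that posture changed over time. If the test were run within each group instead, significance in one and not the other could easily be taken for a group difference that does not exist. In the normal branch the reader cannot tell whether the time effect, the group effect or the interaction will be reported as the answer.

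**Working it through.** **Inputs from the documents.** Two independent groups whose sizes are not fixed; three measurements per woman; about 30 women; significance at p below 0.05. No SD, correlation or effect size is given, and the sample size is not derived from a calculation, so there is no planned figure to reproduce.

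**Step 1: what Friedman uses.** With n women, k conditions and rank sums R_j,

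Q = 12/(nk(k+1)) × ΣR_j² − 3n(k+1).

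Only within-woman ranks enter. For k = 2, with x women increasing, this reduces to Q = (2x − n)²/n, the sign test. With n = 30:

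- All 15 in S rise and all 15 in A fall, the most extreme group difference in direction: x = 15, Q = (30 − 30)²/30 = 0, the smallest possible value.
- All 30 rise, with no group difference in direction: x = 30, Q = (60 − 30)²/30 = 30, the largest possible value.

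The statistic responds to time, not to a group difference in change. Treating the four group-by-time cells as related conditions does not help: S and A are different women, and with unequal groups the test cannot be computed.

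**Step 2: what the ANOVA could be.** With two times, the group-by-time interaction of a mixed ANOVA is the independent t-test on within-woman changes. A valid test is therefore available in the normal branch but is not named.

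**Step 3: size, by simulation.** Assumptions: normal data, SD 1 at each time, equal correlation rho between times, effect at T2 only, 15 versus 15, two-sided 0.05. Results rest on 20,000 simulated studies per scenario (8,000 for rows marked *). Entries are percentages of studies rejecting, except the last row.

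| Scenario and test | rho 0.8 | rho 0.5 | rho 0.3 |
|---|---|---|---|
| **Changes +0.4 and −0.4 SD** | | | |
| Friedman pooled, T0/T1/T2 | 3.1 | 4.3 | 4.4 |
| Friedman pooled, T1/T2 | 2.2 | 3.5 | 3.7 |
| Mann-Whitney on T2−T1 | 90.0 | 52.1 | 40.0 |
| t-test on T2−T1 | 92.1 | 56.2 | 43.0 |
| Mann-Whitney on T2 level* | 53 | 53 | 52 |
| **Only S changes, 0.8 SD** | | | |
| Friedman pooled* | 71 | 40 | 31 |
| **Both change +0.4 SD** | | | |
| Friedman pooled, T0/T1/T2 | 86.1 | 46.8 | 35.7 |
| Friedman pooled, T1/T2 | 75.7 | 38.3 | 28.7 |
| Mann-Whitney on T2−T1 | 4.3 | 4.5 | 4.2 |
| Friedman in each group: exactly one significant | 50.3 | 35.6 | 28.9 |

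Cross-check at rho 0.5: the SD of change is √(2(1 − 0.5)) = 1, so the 0.8 SD difference in change is 0.8 SD of change. The normal approximation gives Φ(0.8 × √(15/2) − 1.96) = Φ(0.231) = 0.59, close to the simulated 0.562 for the t-test; the approximation runs slightly high with 15 per group.

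At 10 versus 20 and rho 0.8, pooled Friedman rejects 12% (opposite changes) and 86% (equal changes), Mann-Whitney on changes 85% and 4%, and exactly one group is significant in 55% under equal change.

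**Step 4: does testing change gain power over testing the T2 level?** For a 0.5 SD difference in change at 15 versus 15, the change t-test has power 20%, 26%, 40%, 55% and 84% at rho 0.3, 0.5, 0.7, 0.8 and 0.9. The level t-test stays at 26% to 27%. The gain depends on the correlation.

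**The case against.** The strongest reply is that the secondary outcome never says difference in change. The Benefits section speaks of identifying parameters that predispose to symptoms in heels, which suggests levels, and the level tests at T1 and T2 answer that validly in both branches. This stands as a possible reading. It does not explain why the plan adds a joint comparison of pre and post in both groups, which would be redundant if levels alone were wanted.

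Several points about the numbers also stand:

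- The 3% figure comes from changes that cancel. If only S changes, pooled Friedman rejects far more often, though still because of time.
- The planned Mann-Whitney at T2 would detect the opposite-change scenario about half the time, so such a difference would not necessarily go unnoticed.
- The main simulation uses normal data, although Friedman applies only when data are judged non-normal. With skewed errors sizes differ (about 80% rather than 47% for equal change at rho 0.5) but the direction is the same. With a larger effect (a total of 0.63 SD between opposite changes, or 0.63 SD in both groups; rho 0.8), skewed errors give pooled Friedman 2.9% and 100%.
- The plan does not say that Friedman would be run within each group. That row shows what happens if it is read so.

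The opening paragraph of the Statistic analysis section also promises independent t-tests between subgroups. It names no variable, sits with the descriptive analysis and has no rank counterpart, so it does not close the gap.

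Finally, an ANOVA on pre and post in two groups is ordinarily a two-factor design. That is fair: the normal-branch half is missing detail, not a wrong test.

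**Conclusion.** The concern holds. In the non-normal branch the plan assigns a group-and-time comparison to a test without a group factor. That follows from the form of the statistic and needs no assumed number. Read as a difference in change, the secondary question has no valid test there. In the normal branch a valid test exists but is unspecified.

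The percentages rest on assumed SD, correlation, group split and effect pattern and are illustrative. Under equal 0.4 SD changes, pooled Friedman rejects in 36% to 86% of studies across rho 0.3 to 0.8, against about 4% for Mann-Whitney on changes. Under opposite changes it stays at 3% to 4%, against 40% to 90%. The primary T1 versus T2 comparison is untouched. The matter is confined to a secondary question in a pilot, but it should be corrected before analysis.

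**What to change.** **Normal branch.** State that the ANOVA is a mixed model with group (S/A), time (T0/T1/T2) and group by time, and that the interaction is the secondary test. Report the between-group contrasts for T2−T1 and T2−T0, each an independent t-test on within-woman changes. This also settles what pre and post mean.

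**Non-normal branch.** Replace Friedman for this purpose with Mann-Whitney on the same changes. Keep Friedman only for T0/T1/T2 in the total group.

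**Both branches.** The level comparisons at T1 and T2 may stay as a question about posture in heels, with a sentence that they are not read as a difference in response. Report estimates with 95% confidence intervals, labelled exploratory, given about 30 women. The reason for the change is that it answers the question; more power is not guaranteed.

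**Cost.** Analysis wording only. All three measurements and group membership are already to be collected.
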